2.4 DETERMINATION OF SAMPLE SIZE

The overall sample size of approximately 70 patients (approximately 50 patients with moderate disease and approximately 20 patients with mild disease) is based primarily on feasibility and clinical considerations, taking into account the limited number of patients with non-severe hemophilia A. This sample size is expected to provide statistically robust point estimates with meaningfully narrow confidence intervals in the overall group of enrolled patients, at the time of the primary analysis or at the time of interim analysis appropriate for regulatory submissions, assuming the same efficacy across dosing regimens.

2.5 ANALYSIS TIMING

An interim analysis and the subsqueent primary analysis will be performed after all 50 patients with moderate hemophilia A have completed respectively 24 weeks of emicizumab treatment and 52 weeks of emicizumab treatment, or are lost to follow-up, or have withdrawn, whichever occurs first.

The final analysis will occur at the end of the study. Additional updates may be performed between the primary and final analysis as might be requested by Health Authorities or deemed necessary by the Sponsor.

3. STATISTICAL METHODS

For continuous variables, means, medians, ranges, and standard deviations will be presented. For categorical variables, the number and percentage of patients within each category will be presented. For each variable (continuous or categorical), the number of available observations will be reported. No formal hypothesis testing will be performed as the study is entirely descriptive.

3.1 ANALYSIS POPULATIONS

3.1.1 All Patients Population

The All patients population includes all patients enrolled in the trial. This population will be used to describe demographic and baseline characteristics.

3.1.2 Treated Population

The Treated population corresponds to all patients who received at least one dose of emicizumab. This population will be the primary population for efficacy and safety analyses.

Emicizumab —F. Hoffmann-La Roche Ltd 9/Statistical Analysis Plan BO41423

3.1.3 Pharmacokinetic-Evaluable Population

The PK-Evaluable population includes all patients who have received at least one dose of emicizumab and have at least one post-baseline emicizumab plasma concentration result.

3.1.4 Up-Titrated Population

Should we have any patients whose dose was up-titrated at least once during the study they will be included in this population.

3.1.5 Immunogenicity Population

The immunogenicity population includes patients with at least one postdose ADA assessment.

3.2 ANALYSIS OF STUDY CONDUCT

The flow of patients through the study will be displayed in a 'CONSORT' diagram. A clear account of all patients who were enrolled, who discontinued the study prematurely, who have ongoing treatment with emicizumab and who completed the study will be provided. In addition, reasons for premature discontinuation from study treatment and reasons for withdrawing from study will be described.

Major protocol deviations (MPD) will be captured in the patient data management systems (PDMS) using the MPD guidance. Number of patients with at least one major protocol deviation, total number of major protocol deviations and the reasons for protocol deviations will be provided. Major protocol deviations could be listed based on health authority requests.

Observation time and duration of follow up, as well as adherence to planned assessment schedule and compliance with data entry into the electronic handheld device, will also be evaluated.

3.3 EFFICACY ANALYSIS

The primary and secondary efficacy analyses will be based on the Treated population. The efficacy objectives of this study will be investigated without any formal hypothesis testing. All analyses will be of descriptive nature only.

3.3.1 Efficacy Period

Efficacy period for each individual patient is defined as the number of days starting from the day of first emicizumab dose to the day of clinical cut-off or withdrawal from the study, whichever is earlier. For patients whose dose is up-titrated, the efficacy period ends a day prior to the first day on the up-titrated dose.

3.3.2 Efficacy Endpoints

3.3.2.1 Bleed Rate

The efficacy of emicizumab is characterized by the number of bleeds over time. This will be calculated using a negative binomial (NB) regression model, which accounts for different follow-up times, with time that each patient stays in the study (efficacy period) included as an offset in the model. In addition, the number of bleeds will also be annualized for each patient using the following formula:

Annualized bleed rate (ABR) = (Number of bleeds/number of days during the efficacy period) \times 365.25.

The mean and median ABR based on the above formula using the observed numbers of bleeds instead of the number resulting from the model will also be calculated. In the case where the negative binomial model does not converge, the alternative derivations of the ABR will be used as the sole method of analysis.

ABR corresponding to treated bleeds, all bleeds, treated joint bleeds, treated target joint bleeds, and treated spontaneous bleeds will be analyzed in a similar manner. These will be summarized for all patients and listed for each patient individually. Several exploratory analyses will be conducted to characterize the type, location, and frequency.

3.3.2.1.1 72-Hour Rule:

Two bleeds of the same type (e.g., "joint", "muscle", or "other") and at the same anatomical location are considered to be one bleed if the second bleed occurs within 72 hours from the last treatment for the first bleed. The last treatment is defined as the last treatment before a new bleed occurs, either in the same or in a different location.

Bleeding rates and characteristics of bleeding describing location and type will also be provided using the 72-hour rule.

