6.5 EFFICACY ANALYSES

6.5.1 Primary Efficacy Endpoint

The key efficacy objective is to characterize the efficacy of emicizumab based on the number of treated bleeds over time. The definition of a treated bleed is described in Section 4.5.7.3.

The clinical effect of prophylactic emicizumab will be assessed via the ABR estimated using a negative binomial regression model, which accounts for different follow-up times, with the number of bleeds from patients as a function of the time such that each patient who stays in the study is included as an offset in the model.

Emicizumab—F. Hoffmann-La Roche Ltd 78/Protocol BO41423, Version 3

The number of bleeds resulting from the model will be annualized for each patient using the following formula:

$$ABR = \left(\frac{Number\ of\ bleeds\ during\ the\ efficacy\ period}{Total\ number\ of\ days\ during\ the\ efficacy\ period}\right) \times 365.25$$

The mean and median ABR based on the above formula using the observed numbers of bleeds instead of the number resulting from the model will also be calculated. In the case where the negative binomial model does not converge, the alternative derivations of the ABR will be used as the sole method of analysis.

A detailed description of the statistical methods and the summaries, if applicable, presented by dosing regimen and/or by disease severity for the efficacy analyses will be provided in the SAP.

6.5.2 Secondary Efficacy Endpoints

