6.5.2.1 Bleed Endpoints

The clinical effect of prophylactic emicizumab on the secondary bleed endpoints of all bleeds (i.e., those treated and untreated with coagulation factors), joint bleeds, target joint bleeds, and spontaneous bleeds (see Section 4.5.7.3 for bleed definitions) will be analyzed in the same manner as for the primary analysis.

The number of bleeds, sites of bleeds, and types of bleeds will be summarized for all patients and listed for each patient individually. Several exploratory analyses will be conducted to characterize the type, location, duration, frequency, and pattern of bleeds. For continuous endpoints, descriptive statistics will be calculated and categorical endpoints will be characterized through frequency tables.

6.5.2.2 Health-Related Quality-of-Life, Patient Preference, Joint Health, Activity, Menstruation Heaviness, and Menstruation-Related Quality of Life

With regards to the PRO secondary objectives, scores by each domain for the CATCH will be computed for each assessment with changes in scores examined for the assessments over time, and these will be summarized descriptively. Patient compliance with the CATCH will be summarized at each assessed timepoint.

For the EmiPref, the proportion of patients/caregivers preferring emicizumab after 17 weeks of treatment will be presented along with the reasons for that choice. Patient/caregivers compliance with the EmiPref will be summarized for Week 17.

For the activity assessment and HJHS, descriptive analyses will be presented by timepoints. All enrolled subjects who contribute to valid activity data (e.g., at least 8 days of wearing the device within a 14-day observation period) will be analyzed for

Emicizumab—F. Hoffmann-La Roche Ltd 79/Protocol BO41423, Version 3

activity. The definition of valid activity data and the handling of missing values will be provided in the SAP.

Relative change from baseline (Weeks 1–2 period) at Weeks 13 (Weeks 12–13 period), 25 (Weeks 24–25 period), 37 (Weeks 36–37 period), and 49 (Weeks 48–49 period) in mean MVPA and DSC will be calculated and summarized. Subject-level data will also be presented at each timepoint.

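### If the negative binomial model fails, the fallback bleed rate weights all patients equally and has no stated interval: a minor gap for rare bleed endpoints, at both the interim and the primary analysis

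*SAP*

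**What the plan says.** SAP 3.3.2.1 fits an NB model with the efficacy period as offset. It also annualizes each patient's observed count over that patient's own days and reports the mean and median of these ABRs. It adds this rule: "where the negative binomial model does not converge, the alternative derivations of the ABR will be used as the sole method of analysis". Protocol 6.5.1 likewise says that "the alternative derivations of the ABR will be used as the sole method of analysis".

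The rule reaches the secondary bleed endpoints. In Protocol 6.5.2.1 they "will be analyzed in the same manner as for the primary analysis"; in the SAP, "treated target joint bleeds, and treated spontaneous bleeds will be analyzed in a similar manner".

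On intervals, SAP 2.4 rests the sample size partly on "narrow confidence intervals in the overall group of enrolled patients, at the time of the primary analysis or at the time of interim analysis". SAP 3.3.2.1 names no CI for any overall bleed rate. The only ABR intervals named are the 95% CIs for subgroups in SAP 3.3.3, without a method. The general rule opening SAP section 3 is "For continuous variables, means, medians, ranges, and standard deviations will be presented".

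On follow-up, SAP 3.3.1 sets no minimum efficacy period, and Protocol 3.1 includes every patient in the primary analysis however short the follow-up. SAP 2.5 places the interim and primary analyses when the 50 moderate patients "have completed respectively 24 weeks of emicizumab treatment and 52 weeks of emicizumab treatment".

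**The concern.** The offset is the only part of the bleed-rate analysis that weights patients by time observed. The fallback drops it, so a patient seen for a week counts as much as one seen for a year. Short follow-up is foreseeable because enrollment of mild patients stays open after the moderate group is full.

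The fallback also has no stated interval. In a descriptive single-arm study the estimate and its interval are the whole result. NB fitting is most fragile when counts are very low, as they may be for treated target joint bleeds. There the plan could leave a mean near 0 with no indication of how high the true rate might be.

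**Working it through.** **Inputs from the documents.** About 70 patients, 50 moderate and 20 mild (SAP 2.4); the two analysis times (SAP 2.5); ABR = bleeds / days × 365.25 (SAP 3.3.2.1); no minimum follow-up. The plan states no rate, dispersion or CI width, so there is no figure of its own to reproduce.

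**Assumptions.** True ABR *m* from 0.02 to 2 and NB dispersion *k* = 1, 3 or 6. Follow-up in years:
- Primary: 50 patients uniform 1–1.5; 20 patients uniform from 1 week (or 4 weeks) to 1. With the 1-week minimum, total *T* ≈ 72.7 patient-years.
- Interim: 50 patients uniform 0.46–0.96; 20 patients from 1 (or 4) weeks to 0.46. With the 1-week minimum, *T* ≈ 40.3.

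**1. What equal weighting can do.** One bleed in 14 days is an ABR of 365.25/14 = 26.1. Take a constructed example: 69 patients with 365 days and 20 bleeds in all, plus one patient with 14 days and 1 bleed.
- Mean ABR: (20 × 365.25/365 + 26.1)/70 = 0.66.
- Pooled rate: 21/(25199/365.25) = 21/69.0 = 0.30.

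This shows sensitivity, not bias. With a constant rate both estimators have the same expectation.

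**2. Precision.** With variance *mt* + *k*(*mt*)² per patient:
- Var(mean ABR) = Σ(*m*/*t* + *km*²)/*n*²
- Var(pooled rate) = Σ(*mt* + *km*²*t*²)/*T*²

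Primary, 1-week minimum: expected Σ1/*t* = 50 × 0.811 + 20 × 4.03 ≈ 121.2, and Σ*t*² = 50 × 1.583 + 20 × 0.340 ≈ 86.0. The 20 shorter-followed patients supply about two thirds of Σ1/*t*.
- *m* = 0.1, *k* = 3: mean (12.12 + 2.10)/4900 = 0.00290, SE 0.054; pooled (7.27 + 2.58)/5285 = 0.00186, SE 0.043; variance ratio 1.56.
- *m* = 2, *k* = 3: mean (242.4 + 840)/4900 = 0.221; pooled (145.4 + 1032)/5285 = 0.223; ratio 0.99.

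Variance ratio at ABR 0.1, range over *k*:

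| | 1-week minimum | 4-week minimum |
|---|---|---|
| Primary | 1.42–1.70 | 1.21–1.38 |
| Interim | 1.51–1.73 | 1.24–1.36 |

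At ABR 2 the range over all settings is 0.92–1.15 (primary) and 0.91–1.24 (interim). These ratios compare the estimators over all trials. They say what is lost if the fallback is used, not how often it is used.

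**3. How often the rule applies.** Intercept-only NB fits in statsmodels: 200 simulated trials per setting, *k* = 3, 1-week minimum, trials with at least one bleed.

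| | Not converged | Converged, no finite SE |
|---|---|---|
| Primary, ABR 0.1 | 4/200 (2.0%) | 47/200 (23.5%) |
| Primary, ABR 0.05 | 5/195 (2.6%) | 102/195 (52.3%) |
| Interim, ABR 0.1 | 4/195 (2.1%) | 62/195 (31.8%) |
| Interim, ABR 0.05 | 8/168 (4.8%) | 96/168 (57.1%) |

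A second set of fits gave about 1–4% and 28–57%. The split depends on the software, and the SAP does not define non-convergence.

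**4. No bleeds at all.** The NB log-rate then has no finite estimate. P(no bleeds) = Π(1 + *kmt*)^(−1/*k*):

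| ABR | Primary | Interim |
|---|---|---|
| 0.1 | 0.1–0.4% | 2.0–3.4% |
| 0.05 | 2.9–4.5% | 14–16% |
| 0.02 | 24–26% | 45–46% |

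Mean and pooled rate are both 0, so only the interval is at issue. The exact Poisson upper limit is −ln(0.025)/*T* = 3.69/*T*: 0.051 per year at 72.7 patient-years and 0.092 at 40.3.

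**5. Does the replacement interval work?** Poisson rate with log-time offset, HC3 robust SE and *t* quantile on *n*−1 df; *n* = 70, at least one bleed. Coverage was about 97% at ABR 0.1, 95–97% at 0.05 and 92–94% at 0.02.

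**The case against.** The strongest reply is that little is lost in practice. The fallback is prespecified and identical in both documents, and the study tests no hypothesis. Outright non-convergence was uncommon in the fits above. Where the NB dispersion estimate is zero, the point estimate already equals total bleeds over total time. The weighting is then intact and, read literally, the fallback is not triggered. The general rule supplies an SD and number of observations, so a reader can form an SE for the mean. The patient listings would also allow the pooled rate to be derived. All of this stands and keeps the point minor. What remains is that the plan commits to no follow-up-weighted fallback and to no interval.

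Four stronger readings are tempting but unsupported:
- **The fallback ignores follow-up or is biased.** Each ABR is divided by the patient's own days, and the mean is unbiased under a constant rate. Weighting and precision are what suffer.
- **The CI is lost because of the fallback.** SAP 3.3.2.1 states no CI for the overall NB rate either.
- **It is an interim problem.** The variance ratios are similar at both analyses, and fits without a finite SE were frequent at both.
- **A median of 0 is a harm of the fallback.** The median is reported whether or not the model converges.

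**Conclusion.** The point holds as a minor, cheap improvement. For rare bleed endpoints the stated fallback is less precise than an available alternative. The more frequent gap is the missing interval, which exists with or without the fallback. If the fallback were used at ABR 0.1, the variance would be about 1.2–1.7 times that of the pooled rate, with no material difference by ABR 2.

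All rates, dispersions and follow-up patterns are assumed, and the convergence figures depend on the software. A reader might infer that the primary result is at risk. The documents do not support that: nothing in them points to treated bleeds overall being this rare, and no test or error rate is involved.

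**What to change.** In SAP 3.3.2.1, state:
- Bleed rates are reported with a 95% CI from the NB model.
- If that model does not converge or gives no finite SE, report total bleeds over total patient-years from a Poisson model with log(efficacy period) as offset, with a robust-SE 95% CI on the log scale (for example HC3 with a *t* quantile).
- With zero bleeds, report 0 with the exact Poisson upper limit 3.69/total patient-years, noting that it ignores overdispersion.
- Mean and median ABR stay as supportive summaries, and intervals in small subgroups are descriptive only.

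Align the matching sentence in Protocol 6.5.1, or record the change in the SAP as a departure from it.

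The cost is a short paragraph and a few lines of code. Intervals will be wide when bleeds are very few. The change does not address bias from up-titration, where SAP 3.3.1 says: "For patients whose dose is up-titrated, the efficacy period ends a day prior to the first day on the up-titrated dose".

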2.2 EFFICACY OBJECTIVES

2.2.1 Primary Efficacy Objective

The primary efficacy objective for this study is to evaluate the efficacy of emicizumab on the basis of the following endpoint:

• Number of treated bleeds over time (i.e., bleed rate)

2.2.2 Secondary Efficacy Objectives

The secondary efficacy objective for this study is to evaluate the efficacy of emicizumab on the basis of the following endpoints:

- Number of all bleeds (i.e., those treated and untreated with FVIII) over time
- Number of joint bleeds over time
- Number of target joint bleeds over time (target joints are defined as joints with ≥3 bleeds occurring in the same joint during the last 24 weeks or unresolved target joints)

An unresolved target joint is defined as a target joint that does not fulfil the criterion of ≤ 2 bleeds into this joint within a consecutive 12-month period.

- Number of spontaneous bleeds over time (spontaneous bleed rate)
- Joint health, as assessed through use of the Hemophilia Joint Health Score (HJHS) at specified timepoints
- Health-related quality of life (HRQoL), as assessed through use of the Comprehensive Assessment Tool of Challenges in Hemophilia (CATCH) Questionnaire over time
- Preference for emicizumab compared with previous FVIII regimen, as assessed through use of the Emicizumab Preference Survey (EmiPref) at Week 17
- Effect of emicizumab prophylaxis treatment on physical activity compared with physical activity at baseline
- Effect of emicizumab prophylaxis treatment on menstruation heaviness and menstruation-related quality of life in female patients of childbearing potential, as assessed through the use of the Menstrual Bleeding Questionnaire (MBQ) and the Menstruation Diary (MD) with the Pictorial Blood Assessment Chart (PBAC) over time

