4.5.7.4 Bleed Definitions and Reporting Definition of a Bleed

For the purpose of the efficacy analyses, a standardized definition of bleed, adapted from criteria defined by the Subcommittee on Standards and Criteria, FVIII/Factor IX subcommittee of the International Society of Thrombosis and Hemostasis, and similar to that used in a recent clinical study, will be used in this study (Blanchette et al. 2014; Mahlangu et al. 2014) as follows:

- An event is considered a treated bleed if coagulation factors are administered to treat signs or symptoms of bleeding (e.g., pain, swelling). An additional definition of all reported bleeds (irrespective of treatment with coagulation factors) will be applied for a separate analysis.
- Bleeds starting from the first sign of bleed and ending 72 hours after the last treatment for the bleed, within which any symptoms of bleeding at the same location or injections are ≤72 hours apart, are considered the same bleed.
- Any injection to treat the bleed, taken > 72 hours after the preceding injection, is considered the first injection to treat a new bleed at the same location.
- Any bleed at a different location is considered a separate bleed regardless of time from last injection.

Definition of Bleed Sites

Bleed sites are defined as follows:

Target joints: defined as a major joint (e.g., hip, elbow, wrist, shoulder, knee, and ankle) into which repeated bleeds occur (frequency of ≥ 3 bleeds into the same joint over the last 24 weeks prior to study entry) or as an unresolved target joint. An unresolved target joint is defined as a target joint that does not fulfil the criterion of ≤ 2 bleeds into this joint within a consecutive 12-month period (Blanchette et al. 2014).

Emicizumab—F. Hoffmann-La Roche Ltd 51/Protocol BO41423, Version 3

- Joint bleeds: defined as bleeds with bleed type "joint bleed" reported via the BMQ with at least one of the following symptoms:
 - Increasing swelling or warmth of the skin over the joint
 - Increasing pain
 - Progressive loss of range of motion or difficulty in using the limb as compared with baseline
- Muscle bleeds (sites as per the BMQ)
- Other (sites as per the BMQ)

Definitions of Bleed Types

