2.3 OBJECTIVES AND ENDPOINTS

2.3.1 Primary Efficacy Objective

The primary efficacy objective for this study is to evaluate the efficacy of emicizumab on the basis of the following endpoint:

• Number of treated bleeds over time (i.e., bleed rate)

2.3.2 Secondary Efficacy Objective

The secondary efficacy objective for this study is to evaluate the efficacy of emicizumab on the basis of the following endpoints:

- Number of all bleeds (i.e., those treated and untreated with FVIII) over time
- Number of joint bleeds over time
- Number of target joint bleeds over time (target joints are defined as joints with
 ≥ 3 bleeds occurring in the same joint during the last 24 weeks)
- Number of spontaneous bleeds over time (spontaneous bleed rate)
- Joint health, as assessed through use of the Hemophilia Joint Health Score (HJHS) at specified timepoints
- Health-related quality of life (HRQoL), as assessed through use of the CATCH Questionnaire over time
- Preference for emicizumab compared with previous FVIII regimen, as assessed through use of the Emicizumab Preference Survey (EmiPref) at Week 17
- Effect of emicizumab prophylaxis treatment on physical activity compared with physical activity at baseline
- Effect of emicizumab prophylaxis treatment on menstruation heaviness and menstruation-related quality of life in female patients of childbearing potential, as assessed through the use of the Menstrual Bleeding Questionnaire (MBQ) and the

Emicizumab —F. Hoffmann-La Roche Ltd 7/Statistical Analysis Plan BO41423

Menstruation Diary (MD) with the Pictorial Blood Assessment Chart (PBAC) over time

2.3.3 Pharmacokinetic Objectives

The Pharmacokinetic (PK) objective for this study is to characterize the emicizumab PK profile on the basis of the following endpoint:

• Plasma concentration of emicizumab at specified timepoints

2.3.4 Safety Objectives

The safety objective for this study is to evaluate the safety profile of emicizumab in patients with non-severe hemophilia A without inhibitors on the basis of the following endpoints:

- Incidence and severity of adverse events, with severity determined according to WHO Toxicity Grading Scale
- Incidence of thromboembolic events
- Incidence of thrombotic microangiopathy (TMA)
- Change from baseline in physical examination findings
- Change from baseline in and vital signs
- Change from baseline in ECG parameters
- Incidence of laboratory abnormalities

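### SAP 3.3.2.1 analyses only treated joint, target-joint and spontaneous bleeds, although the protocol and SAP 2.3.2 state these three secondary endpoints without a treatment condition

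*SAP*

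**What the plan says.** Protocol 2.2.1 and 2.2.2 mention treatment in two bleed endpoints. The primary endpoint is "Number of treated bleeds over time (i.e., bleed rate"), and the first secondary endpoint is "Number of all bleeds (i.e., those treated and untreated with FVIII) over time". The next entries have no such condition: "Number of joint bleeds over time", "Number of target joint bleeds over time" and, in the same unqualified form, spontaneous bleeds.

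Protocol 4.5.7.4 gives the operational definitions. The joint entry begins "Joint bleeds: defined as bleeds with bleed type" and goes on to require a joint-bleed report in the Bleed and Medication Questionnaire (BMQ) plus at least one listed symptom. A target joint is defined by how many bleeds have occurred into it. A spontaneous bleed is one for which the patient knows of no trigger. A treated bleed is defined separately, as one for which coagulation factor was given.

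Protocol 6.5.2.1 names the secondary analysis variables, after all bleeds, as "joint bleeds, target joint bleeds, and spontaneous bleeds".

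The SAP first repeats the protocol's list. SAP 2.3.2 has, for example, "Number of spontaneous bleeds over time (spontaneous bleed rate"), again without a treatment condition. SAP 3.3.2.1 then specifies: "ABR corresponding to treated bleeds, all bleeds, treated joint bleeds, treated target joint bleeds, and treated spontaneous bleeds will be analyzed".

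**The concern.** Three secondary endpoints are stated one way and analysed another, and the SAP does not remark on the change. A symptomatic joint bleed managed without coagulation factor meets the protocol's definition of a joint bleed but would not enter the joint-bleed ABR. Such a bleed is possible under the plan, because protocol 4.4.1 permits other agents, such as DDAVP or antifibrinolytics, to control bleeds.

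The study is single-arm and descriptive, so the estimated rates are themselves the result. A rate reported under an endpoint's name should measure that endpoint. Protocol 1.1 presents joint bleeding as central to the disease and links repeated bleeding into joints to chronic arthropathy, so the joint-bleed rate will be read closely.

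**Working it through.** There is no planned figure to reproduce. The documents give no assumed bleed rate, dispersion or untreated share, and no power calculation. The check is a comparison of texts, followed by one line of algebra.

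**Step 1. Treatment condition attached to each endpoint, by place.**

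| Place | Primary | All bleeds | Joint | Target joint | Spontaneous |
|---|---|---|---|---|---|
| Protocol 2.2.1 and 2.2.2 | treated | treated and untreated | none | none | none |
| Protocol 4.5.7.4 (definitions) | coagulation factor given | irrespective of treatment | none (type and symptom) | none (bleed count) | none (no known trigger) |
| Protocol 6.5.2.1 | not listed | treated and untreated | none | none | none |
| SAP 2.3.1 and 2.3.2 | treated | treated and untreated | none | none | none |
| SAP 3.3.2.1 | treated | all | **treated** | **treated** | **treated** |

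Only the last row restricts the last three columns. SAP 3.3.2.1 therefore differs from the protocol and from SAP 2.3.2.

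**Step 2. Could protocol 6.5.2.1 bring in the restriction?** It says the secondary bleed endpoints are analysed the same way as the primary one. The same sentence covers all bleeds, which include untreated ones, so it can refer only to the statistical method and not to the treated condition.

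**Step 3. Could the protocol version explain it?** The SAP reproduces the synopsis of protocol version 2, while the current protocol is version 3. That version 2 synopsis also lists the three endpoints without a treatment condition, so the version gap is not the cause.

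**Step 4. Is the unrestricted rate planned elsewhere?** The subgroup summaries in SAP 3.3.3 cover treated bleeds and all bleeds only. The exploratory work on type, location and frequency, and the 72-hour-rule summaries by location and type, do not specify an ABR for joint, target-joint or spontaneous bleeds irrespective of treatment.

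**Step 5. Direction and size.** Let N be the number of bleeds of one kind over D patient-days, and u the share of them that received no coagulation factor.

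- Stated endpoint: ABR = (N / D) × 365.25
- SAP endpoint: ABR = (N(1 − u) / D) × 365.25
- Ratio of SAP to stated endpoint: 1 − u, which is at most 1

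The documents do not give u. With assumed values and an ABR of 1.0 under the stated endpoint:

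| Assumed u | Treated-only ABR |
|---|---|
| 20% | 1.0 × (1 − 0.2) = 0.8 |
| 40% | 1.0 × (1 − 0.4) = 0.6 |
| 60% | 1.0 × (1 − 0.6) = 0.4 |

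The ratio is exact for the crude rate before nearby events are merged. The negative binomial estimate weights patients by follow-up and dispersion, so it need not follow the ratio exactly.

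**The case against.** **Treated as the default.** The strongest contrary reading comes from protocol 4.5.7.4. It defines the treated bleed first and then adds a definition of all reported bleeds for use in an analysis of its own. That could mean that every endpoint counts treated bleeds except the single all-bleeds analysis, which is what the SAP's list does. Protocol 6.5.1 also leaves detailed methods to the SAP. This reading is possible but weaker. No endpoint, site or type definition adopts the default, and if it applied, the primary endpoint would not need the word treated. It does mean that the protocol is silent on the matter and does not expressly forbid the restriction.

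**Nothing is lost.** A reader might infer that untreated joint and spontaneous bleeds disappear from the results. The documents do not support that. These bleeds count in the all-bleeds ABR, and protocol 6.5.2.1 plans summaries and patient listings of bleed numbers, sites and types with no treated restriction. What remains is that the all-bleeds ABR pools every site and cause, so it cannot supply the three specific rates.

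**Open-label bias.** A reader might also infer that knowing they receive emicizumab, or the instruction to use the smallest effective FVIII dose, leads patients not to infuse, and that the restriction therefore builds in bias. The documents do not establish this. The dose instruction concerns how much FVIII is given once a bleed is treated, not whether to treat it. The same argument would apply to the protocol's own primary endpoint. Untreated bleeds are themselves patient-reported without blinding, and the patient judges what counts as strenuous activity. The point therefore makes no claim about what drives the decision to treat.

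**Little depends on it.** SAP section 3 rules out formal hypothesis testing. That limits the importance of the mismatch but does not remove it.

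**Conclusion.** The mismatch stands. SAP 3.3.2.1 narrows three secondary endpoints to treated bleeds, without a stated reason, against the wording of protocol 2.2.2, 4.5.7.4 and 6.5.2.1 and of SAP 2.3.2. As written, the plan specifies no ABR for joint, target-joint or spontaneous bleeds as those endpoints are worded.

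The effect on the crude rate runs in one direction: the treated-only figure equals the stated endpoint's figure if every such bleed is treated, and is lower otherwise. Its size cannot be fixed from the documents; the values in the table above illustrate it and are not estimates. The conclusion rests on reading the endpoint lists literally, which the explicit treatment wording in the primary and all-bleeds endpoints supports. The matter should be corrected, but it concerns secondary, descriptive results and leaves the primary analysis untouched.

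**What to change.** In SAP 3.3.2.1, report the joint, target-joint and spontaneous ABRs irrespective of treatment with coagulation factor, matching the stated endpoints. Keep the three treated-only ABRs as supplementary analyses, labelled as such.

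Also state how the 72-hour rule applies. In SAP 3.3.2.1.1 the window runs from the last treatment of the first bleed, so an untreated bleed gives it no starting point. The SAP should say when two reports at the same site count as one bleed if the first was untreated. The all-bleeds ABR already needs this rule.

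If the sponsor did intend treated bleeds only, the endpoint wording in protocol 2.2.2 and 6.5.2.1 and SAP 2.3.2 would have to say so, with a reason.

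The cost is three extra ABR rows from BMQ data already collected, one added counting rule, and secondary rates that may look somewhat less favourable.
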